2.1 Minimization of Risk

In clinical trials with reproxalap topical ocular solution in various strengths in different ocular indications, no safety signal or treatment-related SAE's have been observed (Section 2). Generally mild to moderate transient ocular discomfort and ocular stinging, lasting only up to a few minutes, was the most frequently reported AE.

In addition, extensive in vitro and in vivo studies conducted to assess the safety, efficacy, and pharmacokinetics of reproxalap have shown that reproxalap is effective in animal models of inflammation, is not toxic to the eye, and can achieve therapeutically relevant concentrations in the eye. Nonclinical safety and toxicology studies of reproxalap administration by several routes of administration have consistently demonstrated reproxalap to be well tolerated, with no significant adverse findings at significant dose multiples of those expected in planned clinical trials. In aggregate, the nonclinical studies completed to date provide compelling evidence that reproxalap has the potential to ameliorate pathologic ocular inflammation without off-target pharmacological or toxic effects. Please refer to the Investigator's Brochure for additional information.

3 STUDY OBJECTIVES

The study objectives are as stated below:

- To evaluate the safety and efficacy of Reproxalap 0.25% Ophthalmic Solution compared to Vehicle Ophthalmic Solution for the treatment of dry eye disease.
- Part 1 will confirm the dosing regimen (four times daily (QID) dosing for 12 weeks, or QID dosing for four weeks followed by twice-daily (BID) dosing for weeks 5-12) to be utilized in Part 2 of this adaptive Phase 3 clinical trial.
- Part 1 will confirm the sample size to be utilized in Part 2 of this adaptive Phase 3 clinical trial.

4 CLINICAL HYPOTHESES

The clinical hypothesis is that Reproxalap 0.25% Ophthalmic Solution is more effective than vehicle in reducing the signs and symptoms of DED.

5 OVERALL STUDY DESIGN

The clinical trial is an adaptive Phase 3, multi-center, randomized, double-masked, parallel-group, vehicle-controlled design with block enrollment, and is comprised of two parts (Part 1 and Part 2). Test article will be self-administered topically to the eye.

Screening

Prior to randomization into either Part 1 or Part 2, subjects will receive 14 consecutive days (± 2) of vehicle, self-administered QID in both eyes, between Visits 1 and 2. Subjects randomized in Part 1 will not be eligible to participate in Part 2.

During the screening period (Visit 1 to Visit 2), two 90-minute exposures in the CAE[®] will be conducted to ascertain eligibility. Subjects who qualify will be randomized to receive study drug in a double-masked fashion for 84 days. At Visits 3 - 9, no CAE[®] exposure will occur but signs and symptoms will be assessed.

Part 1

Subjects will be randomized 1:1:1:1 into one of four treatment arms (100 subjects per arm):

A1. Reproxalap administered QID for twelve weeks

A2. Vehicle administered QID for twelve weeks

B1. Reproxalap administered QID for four weeks, followed by BID administration for eight weeks

B2. Vehicle administered QID for four weeks, followed by BID administration for eight weeks

The results of A1 will be compared to the results of A2. The results of B1 will be compared to the results of B2.

Subjects, the Sponsor, the CRO, investigators, and site personnel will be masked to treatment assignment. Subjects will not be masked to dosing regimen.

The total number of expected participants in Part 1, including screen failures, is approximately 1,000 subjects. The duration of Part 1 is approximately 14 weeks (98 days), including 12 weeks of treatment.

Part 2

Subjects will be randomized 1:1 to receive treatment with either reproxalap or vehicle for twelve weeks. Dosing regimen and subject number per arm will be determined based on the results of Part 1. The duration of Part 2 is approximately 14 weeks (98 days), including 12 weeks of treatment.

Subjects, the Sponsor, the CRO, investigators, and site personnel will be masked to treatment assignment.

Subjects who terminate early during the treatment period will be asked to complete safety assessments prior to commencement of alternative DED therapy (if possible). Subjects who are terminated early from the study will not be replaced.

6 STUDY POPULATION

6.1 Number of Subjects (approximate)

It is estimated that approximately 1,000 subjects will be screened to enroll approximately 400 randomized subjects (100 in each group) for Part 1.

The number of subjects in Part 2 will be statistically powered based on the results of Part 1.

Subjects randomized in Part 1 will not be eligible to participate in Part 2.

6.2 Study Population Characteristics

All subjects must be at least 18 years of age, and must meet all inclusion criteria and none of the exclusion criteria.

6.4 Exclusion Criteria

Each subject must not:

- 1. Have any clinically significant slit-lamp findings at Visit 1, including active blepharitis; meibomian gland dysfunction (MGD); lid margin inflammation; or active ocular allergies that require therapeutic treatment, or, in the opinion of the investigator may interfere with the assessment of the safety or efficacy of reproxalap or vehicle;
- 2. Have or be diagnosed with an ongoing ocular infection (bacterial, viral, or fungal) or active ocular inflammation at Visit 1;
- 3. Have worn contact lenses within 7 days of Visit 1 or anticipate using contact lenses during the study;
- 4. Have used any eye drops within 2 hours of Visit 1;
- 5. Have previously had laser-assisted in situ keratomileusis (LASIK) surgery within the last 12 months;
- 6. Have used ophthalmic cyclosporine or lifitigrast 5.0% ophthalmic solution within 90 days of Visit 1;
- 7. Have any planned ocular and/or lid surgeries over the study period or any ocular surgery within 6 months of Visit 1;
- 8. Have used temporary or permanent punctal plugs within 30 days prior to Visit 1 or anticipate their use during the study period;
- 9. Be currently taking any topical ophthalmic prescription (including medications for glaucoma) or over-the-counter (OTC) solutions, artificial tears, gels or scrubs, that cannot be discontinued for the duration of the trial (excluding medications allowed for the conduct of the study);
- 10. Have corrected visual acuity (VA) greater than or equal to the logarithm of the minimum angle of resolution (logMAR) as assessed by Early Treatment of Diabetic Retinopathy Study (ETDRS) scale in both eyes at Visit 1;
- 11. Be a woman who is pregnant, nursing, or planning a pregnancy during the trial;
- 12. Be unwilling to submit a urine pregnancy test at Visit 1 and Visit 9 (or early termination visit) if of childbearing potential. Non-childbearing potential is defined as a woman who is permanently sterilized (e.g., has had a hysterectomy or tubal ligation), or is post-menopausal (without menses for 12 consecutive months);
- 13. Be a man or woman of childbearing potential who is not using an acceptable means of birth control; acceptable methods of contraception include: hormonal oral, implantable, injectable, or transdermal contraceptives; mechanical spermicide in conjunction with a barrier such as a diaphragm or condom; intrauterine device (IUD); or surgical sterilization of males or partner. For non-sexually active males or females, abstinence may be regarded as an adequate method of birth control; however, if the subject becomes sexually active during the study, he/she must agree to use adequate birth control as defined above for the remainder of the study;

- Have a known allergy and/or sensitivity to reproxalap or the test article excipients;
- 15. Have a condition or be in a situation which the investigator feels may put the subject at significant risk, may confound the study results, or may interfere significantly with the subject's participation in the study;
- 16. Be currently enrolled in an investigational drug or device study or have used an investigational drug or device within 30 days of Visit 1;
- 17. Have previously participated in a reproxalap ophthalmic solution study;
- 18. Be currently using any medication known to cause ocular drying that has not been used on a stable dosing regimen for at least 30 days prior to Visit 1;
- 19. Be unable or unwilling to follow instructions, including participation in all study assessments and visits.

6.5 Withdrawal Criteria (if applicable)

If at any time during the study the investigator determines that a subject's safety has been compromised, the subject may be withdrawn from the study.

Subjects may withdraw consent from the study at any time.

The Sponsor and investigators may discontinue any subject for non-compliance, or for any medical reason.

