In 1995, Augustin et al. (Augustin 1995) described elevations in tear MDA levels that correlated with severity in DED patients. Subsequently, Choi et al. (Choi 2016) reported that expression of MDA and 4-hydroxynonenal (another RASP commonly associated with inflammation) is increased in the tear film and ocular surface of patients with DED. Consistent with the literature that supports the notion that RASP mediate pro-inflammatory toxicity in DED, the anti-inflammatory effects of the RASP scavenger reproxalap have been demonstrated in Phase 2 clinical trials in DED, noninfectious anterior uveitis, and allergic conjunctivitis. In aggregate, a broad array of preclinical and clinical evidence supports the use of reproxalap for the treatment of ocular inflammation, including DED.

2 Clinical Studies of Reproxalap Ophthalmic Solution

Reproxalap ophthalmic solution is in clinical development for the treatment of ocular inflammation. The drug product, in various strengths, has completed a Phase 1 clinical trial, as well as a vehicle-controlled, double-masked Phase 2a clinical trial in allergic conjunctivitis; a vehicle-controlled, double-masked Phase 2b clinical trial in allergic conjunctivitis; a comparator-controlled, investigator-masked Phase 2 clinical trial in noninfectious anterior uveitis; a vehicle-controlled, double-masked Phase 2b clinical trial in DED; and a vehicle-controlled, double-masked Phase 2b clinical trial in DED. Phase 3 clinical trials in noninfectious anterior uveitis and allergic conjunctivitis are in progress. A total of 468 subjects have been exposed to topical ocular reproxalap in completed clinical trials.

In all clinical trials, no treatment-related serious adverse events (SAE) have been observed. Generally mild to moderate transient ocular stinging, lasting only up to a few

minutes, was reported in most subjects treated in the Phase 1 and the allergic conjunctivitis and dry eye disease Phase 2 clinical trials, and in a small proportion of subjects in the noninfectious anterior uveitis Phase 2 and the allergic conjunctivitis Phase 2b clinical trials. Table 1 summarizes the clinical exposure to topical ocular reproxalap for completed clinical trials.

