9.3.11 Early Termination/Discontinuation

If a subject is discontinued from the study prior to Visit 9 (Day 85 ± 3), then all safety evaluations that are to be performed at Visit 9 should be performed on the day of discontinuation (early termination) or at the discretion of the investigator.

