9.6.2 Discontinued Subjects

Subjects may be discontinued prior to their completion of the study due to:

- subject request/withdrawal
- AEs
- protocol violations
- administrative reasons (e.g., inability to continue, lost to follow up)
- Sponsor termination of study
- other

Note: In addition, any subject may be discontinued for any sound medical reason.

Notification of a subject discontinuation and the reason for discontinuation will be made to Ora and/or Sponsor and will be clearly documented on the eCRF.

9.7 **Study Termination**

The study may be stopped at any time by the investigator, the Sponsor, and/or Ora with appropriate notification.

9.8 **Study Duration**

An individual subject's participation will involve nine visits over approximately a 14week (~98 days) period (84 days of treatment and 14 days pre-screening).

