10.3.2 Reporting a Serious Adverse Event

To ensure subject safety, all SAEs, regardless of relationship to the IP, must be immediately reported. All information relevant to the SAE must be recorded on the appropriate CRFs. The investigator is obligated to pursue and obtain information requested by Ora and/or the Sponsor in addition to that information reported on the CRF. All subjects experiencing a SAE must be followed up and the outcome reported.

In the event of a SAE, the investigator must notify Ora and the Sponsor immediately; obtain and maintain in his/her files all pertinent medical records, information, and medical judgments from colleagues who assisted in the treatment and follow-up of the subject; provide Ora and the Sponsor with a complete case history, which includes a statement as to whether the event was or was not suspected to be related to the use of the IP; and inform the IRB/IEC of the SAE within their guidelines for reporting SAEs.

Contact information for reporting SAEs:

10.4 **Procedures for Unmasking (if applicable)**

All subjects, investigators, and study personnel involved with the conduct of the study will be masked with regard to study drug treatment assignments. When medically necessary, the investigator may need to determine what treatment has been assigned to a subject. When possible (i.e., in non-emergent situations), Ora and/or the Sponsor should be notified before unmasking IP. Ora and/or the study Sponsor must be informed immediately about any unmasking event.

If an investigator identifies a medical need for unmasking the treatment assignment of a subject, he/she should contact Ora and/or the medical monitor prior to unmasking the identity of the IP, if possible. Ora will ask the site to complete and send them the Unmasking Request Form. Ora will notify Aldeyra and jointly will determine if the unmasking request should be granted. They may consult the medical monitor as needed.

Confidential

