The result of the request will be documented on the Unmasking Request Form. If approval is granted to unmask a subject, written permission via the Unmasking Request Form will be provided to the investigator. The investigator will unmask the subject using IWRS. The investigator will complete the Unmasking Memo form and include it in the subject's study file and provide a copy for the TMF. For each unmasked request, the reason, date, signature, and name of the person who unmasked the subject, must be noted in the subject's study file.

Unmasked subjects will be discontinued from the study.

10.5 **Type and Duration of the Follow-up of Subjects after Adverse Events**

The investigator will follow unresolved AEs to resolution until the subject is lost to follow-up or until the AE is otherwise classified. Resolution means the subject has returned to baseline state of health or the investigator does not expect any further improvement or worsening of the AE. If the subject is lost to follow-up, the investigator should make three reasonable attempts to contact the subject via telephone, post, or certified mail. All follow-up will be documented in the subject's source document. Non-serious AEs identified on the last scheduled contact must be recorded on the AE eCRF with the status noted.

If the investigator becomes aware of any new information regarding an existing SAE (i.e., resolution, change in condition, or new treatment), a new SAE/Unanticipated Report Form must be completed and faxed to Ora within 24 hours of the site's awareness of the new information. The original SAE form is not to be altered. The report should describe whether the event has resolved or continues and how the event was treated.

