7.1 Intent-to-Treat

Intent-to-Treat Population: The intent-to-treat (ITT) population includes all randomized subjects. Subjects in the ITT population will be analyzed as randomized. In addition, two populations are further defined for the primary analysis:

- ITTOD Population The ITTOD population includes subjects in the ITT population with baseline ocular dryness score ≥ 3 (Ocular Discomfort and 4-Symptom Questionnaire).
- ITTFSN Population The ITTFSN population includes subjects in the ITT population with baseline fluorescein nasal staining score ≥ 2.

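### Removal from the study for non-compliance, protocol violations or unmasking ends co-primary data collection that could have continued

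*Protocol*

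**What the plan says.** Three rules take a randomised subject out of the study, as distinct from off the drops.

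- Protocol 6.5: "The Sponsor and investigators may discontinue any subject for non-compliance, or for any medical reason". No compliance threshold is given there.
- Protocol 9.6.2: "Subjects may be discontinued prior to their completion of the study due to" a list of reasons that includes adverse events and protocol violations.
- Protocol 10.4, repeated in SAP 4.2: "Unmasked subjects will be discontinued from the study". Unmasking itself is confined to medical need: "When medically necessary, the investigator may need to determine what treatment has been assigned to a subject".

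At early exit, Protocol 9.3.11 asks that "all safety evaluations that are to be performed at Visit 9 should be performed on the day of discontinuation", or at the investigator's discretion. It names no efficacy assessment and no later visit. Protocol 5 likewise asks only for safety assessments and adds: "Subjects who are terminated early from the study will not be replaced".

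On the analysis side, SAP 7.1 states: "The intent-to-treat (ITT) population includes all randomized subjects". ITTOD and ITTFSN are subsets of that population defined by baseline score. SAP 8.2 and Protocol 11.4.3 run the co-primary MMRM on those two populations with observed data only. SAP 13.1.1 and 13.1.2 add two multiple-imputation sensitivity analyses for each co-primary endpoint: MCMC under missing at random, and a control-based pattern-mixture model under missing not at random.

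**The concern.** A subject who skips doses or breaches the protocol has not necessarily refused further visits. Where the study ends that subject's participation, the later dryness and staining scores are missing because of a study rule. That is avoidable missing data in a primary analysis meant to represent everyone randomised.

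The loss could also be informative. Protocol 2 reports that transient stinging "was reported in most subjects treated in the Phase 1 and the allergic conjunctivitis and dry eye disease Phase 2 clinical trials". A subject who finds the drops uncomfortable may skip them and then be removed for non-compliance. If that happened more often on reproxalap, and those subjects would have done worse than those who stayed, the observed-data MMRM would extrapolate too much benefit to them. Part 1 estimates also set the Part 2 sample size (SAP 5), so an overstated effect would carry forward.

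**Working it through.** **Step 1. Set the rules beside the data flow.**

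| Ground | Where | Force | Efficacy visits afterwards |
|---|---|---|---|
| Non-compliance | Protocol 6.5 | permissive | none provided |
| Protocol violation | Protocol 9.6.2 | permissive | none provided |
| Unmasking | Protocol 10.4, SAP 4.2 | mandatory | none provided |

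No section describes stopping drops while staying in follow-up. With observed data only, a removed subject contributes scores up to removal and nothing after it. Removal is not needed to protect the analysis. SAP 7.2 already excludes significant deviations from the per-protocol populations, SAP 9 summarises major deviations, and SAP 12.1 classifies compliance as below 80%, 80% to 125%, or above 125%.

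**Step 2. Reproduce the plan's sample sizes.** Inputs from SAP 5 and 8.4 are two-sided alpha 0.05, power 90% and 4 repeated measures. Staining has difference 0.2967, SD 0.53 and correlation 0.5749. Dryness has 0.3952, 0.73 and 0.7783. The variance factor for the mean of four measures under first-order autoregressive correlation is f = [4 + 2(3ρ + 2ρ² + ρ³)]/16, and n per arm = 2[SD·√f·(1.960 + 1.282)/difference]².

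- Staining: f = 0.572, n = 38.35, so 39. The SAP says 39.
- Dryness: f = 0.752, n = 53.94, so 54. The SAP says 54.

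The documents do not name the correlation structure. I infer the autoregressive form because compound symmetry gives 46 and 60 and does not match. These figures only confirm that the planning effects are read correctly. They say nothing about removals.

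**Step 3. Illustrate the possible size.** The documents give no removal rate for reproxalap 0.25%. Assume that a fraction p of the active arm is removed before Week 2, that these subjects would have had vehicle-like outcomes, that no vehicle subjects are affected, and that the MMRM extrapolates the full effect to those removed. The effect across all randomised subjects is then (1 − p) × the planned effect, and the overstatement factor is 1/(1 − p).

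| p (assumed) | Staining effect, all randomised | Overstatement factor |
|---|---|---|
| 0% | -0.2967 | 1.000 |
| 5% | 0.95 × -0.2967 = -0.282 | 1.053 |
| 10% | 0.90 × -0.2967 = -0.267 | 1.111 |
| 15% | 0.85 × -0.2967 = -0.252 | 1.176 |

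The same factors apply to dryness. Later removal gives a smaller discrepancy, because data before removal stay in the model.

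**Step 4. What the smaller effect would mean for power.** Use power = Φ(effect/(SD·√f·√(2/n)) − 1.960), with SD held fixed and p = 10%. Staining falls from 90.5% to 83.7% at 39 per arm, and from 99.9% to 99.7% at 100 per arm. Dryness falls from 90.0% to 83.1% at 54 per arm, and from 99.3% to 97.8% at 100 per arm. The 100-per-arm values are upper bounds, because ITTOD and ITTFSN are subsets of each arm.

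**The case against.** A reader might infer that the plan cuts off data because of drop irritation, and that this favours reproxalap. The documents do not support either statement.

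- No section ties non-compliance, protocol violations or unmasking to irritation. Protocol 2 describes the stinging as generally mild to moderate and lasting at most a few minutes, and gives no comparison with vehicle. Its count of 11 of 12 discontinuations for irritation comes from a trial of 0.1% and 0.5% formulations with 17 subjects per group. For the trial that included 0.25%, it reports no evident safety concern.
- The direction is open. Removing poorly responding vehicle subjects would push the estimate the other way.
- Two of the three rules are permissive. Sponsor and site staff are masked to treatment, which limits selective removal, although stinging might hint at the assignment. Unmasking needs a medical reason and an approval step, so it is unlikely to involve many subjects.
- The ITT definition is met as written: all randomised subjects, analysed as randomised. The documents do not state a treatment-policy estimand.
- The control-based pattern-mixture analyses examine the vehicle-like scenario of Step 3 for both co-primaries and have their own tables in SAP 18. The question is therefore not left unexamined.

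All of this stands, and it limits the point. It does not remove it. The pattern-mixture analyses are sensitivity analyses, the success criterion rests on the observed-data MMRM, and imputation is a poor substitute for scores that a willing subject could have given at a scheduled visit.

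**Conclusion.** The point holds in a limited form. It is certain from the text that the rules allow, and after unmasking require, exit from the study with no further efficacy visits, and that the co-primary MMRM then has no later data for those subjects. It is plausible but not shown that the resulting gaps depend on tolerability. The link, its direction and its size are all unknown.

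The reductions of 5% to 15% in the all-randomised staining effect illustrate the assumptions in Step 3. They are not estimates of bias in this trial. The defect does not invalidate the primary analysis. It is an avoidable source of missing data that is cheap to close.

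**What to change.** 1. In Protocol 6.5 and 9.6.2, state that non-compliance and protocol violations alone do not end study follow-up. Such subjects are asked to continue the scheduled visits, with VAS dryness, nasal staining and safety collected.
2. In the SAP, state that these observations stay in ITTOD and ITTFSN and that the deviations act only through the per-protocol populations. Those populations now also require completion, so a subject who is followed to Week 12 must be excluded through the significant-deviation classification instead.
3. In Protocol 10.4 and SAP 4.2, allow unmasked subjects to be asked to continue visits, with unmasked status flagged in the eCRF. Dryness is subject-reported and could be influenced by knowing the treatment, so whether post-unmasking VAS data enter the primary analysis is a trade-off for the sponsor to settle in advance.
4. Leave unchanged the medical and safety withdrawal rules, consent withdrawal, sponsor termination, administrative reasons, and any decision about stopping drops.

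The cost is amendment wording, a sentence or two in the SAP, one eCRF flag, and a few visits already in the schedule. The estimate may also be less favourable if the retained subjects do poorly. If the change comes too late for Part 1, the wording still serves Part 2, whose SAP is to be finalised after Part 1 database lock (SAP 1).
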